5.1.2 Additional study treatment

No additional treatment beyond study treatment is requested for this trial.

Patients will continue to use their background medication i.e H1-AH at approved or increased doses alone or in combination with H2-AH and/or a LTRA (standard of care) with a stable regimen during the study.

[figure not shown]

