5.5.6 Rescue medication

Fexofenadine, loratadine, and cetirizine (H1-AH), in addition to being used as background medication will be allowed as rescue medication and used on an as needed basis during treatment and follow-up epochs. The selection of any one rescue medication should be made once for an individual patient. A switch of the rescue medication for an individual patient or between the core and extension study is not permitted. The patients will use the rescue medication at the indicated dose. If required for symptomatic relief, patients may take up to 4x the approved dose of the rescue medication, depending on local clinical practice and guideline. H1-AH rescue medication will be sourced locally.

As an additional safety precaution for the treatment of anaphylactic reactions, patients will be supplied with epinephrine, either via an auto-injector (if available) or as per other local standard of care. The investigator will train the patients on how to detect such reactions and how to use epinephrine. After any use of epinephrine, patients will need to seek immediate medical attention to ensure that the initial reaction has been successfully controlled and/or to trigger additional therapeutic steps.

The use of epinephrine will be recorded on the concomitant medication CRF page.

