5.5.7 Concomitant treatment

This study requires concurrent use of H1-AH alone (at approved doses as per local health authority guidance or at increased doses up to four-fold) or in combination with H2-AH and/or LTRA (montelukast, zafirlukast, pranlukast) as background medication.

It is recommended that patients should remain on a stable treatment regimen (H1-AH alone or in combination with H2-AH and/or LTRA) throughout the study.

The investigator should instruct the patient to notify the study site about any new medications he/she takes after the patient was enrolled into the study. All medications, procedures and significant non-drug therapies (including physical therapy and blood transfusions) administered after the patient was enrolled into the study must be recorded on the respective CRF pages.

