9.3 Treatments

The number of patients and the length of time (in days) exposed to study drug will be summarized by treatment for the safety set.

Concomitant medications will be summarized for the safety set separated for urticaria related background medications and non-urticaria related medications. Urticaria related background medications will be summarized by pre-specified categories (including dose) and preferred term. Non-urticaria related concomitant medications will be summarized by preferred term. Use of rescue medication will be summarized as well.

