2.4.2 Prior and concomitant therapies

Prior and concomitant medication / surgery and medical procedures

Prior medications are defined as treatment taken and stopped prior to first dose of the core study drug. Prior medications were reported and analyzed in the core study and will not be reported in the extension study.

Listings will be provided for the medications and for the significant surgeries and medical procedures which were ongoing at the end of the core study or started after the end of the core study, and ended prior to first dose of the extension study drug.

Concomitant medications are defined as any medication given at least once after the first day of first extension study drug dose, and will be summarized on the safety set.

In case of missing end date the medication will be considered as concomitant. If it is partially missing, then the medication month and year will be compared to the month and year of the

first injection date, to know if the medication stopped prior to the drug or not. In case of uncertainty the medication will be considered as concomitant.

Medications will be identified using the Novartis Drug and Therapy Dictionary (NovDTD) including the Anatomical Therapeutic Chemical (ATC) code. Medications will be presented in alphabetical order, by ATC code.

Concomitant medications for CSU starting or continuing during the treatment epoch or during the follow-up epoch will be summarized for each epoch, by type of therapy, ATC code, preferred term and symptom treated. Non-urticaria related concomitant medications starting or continuing during the treatment epoch or during the follow-up epoch will be summarized for each epoch, by ATC code and preferred term.

Concomitant significant surgeries and medical procedures starting or continuing during the treatment epoch or during the follow-up epoch will be summarized for each epoch, by primary system organ class and MedDRA preferred term.

Concomitant use of rescue medication

Concomitant use of rescue medication (using eCRF information) starting during the treatment epoch or during the follow-up epoch will be summarized for each epoch, by ATC code and preferred term.

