2.5.5 Statistical model, hypothesis, and method of analysis

No hypotheses will be tested as per the protocol. All the analysis will have a descriptive purpose.

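### SAP 2.4.2 counts eCRF rescue medication only in the epoch where it starts, does not restate the protocol's dose categories for background therapy, and leaves out drugs given only on Day 1

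*SAP*

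**What the plan says.** **Rescue.** Protocol 9.3 plans a summary of rescue use and sets no condition on start date. SAP 2.4.2 narrows this for the eCRF data: "Concomitant use of rescue medication (using eCRF information) starting during the treatment epoch or during the follow-up epoch will be summarized for each epoch". In the same section, CSU medications, non-urticaria medications, and surgeries and procedures are each summarized per epoch if they start in the epoch or continue into it. Rescue is one H1-antihistamine per patient, chosen once: "A switch of the rescue medication for an individual patient or between the core and extension study is not permitted".

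**Background dose.** Protocol 9.3 states: "Urticaria related background medications will be summarized by pre-specified categories (including dose) and preferred term". SAP 2.4.2 classifies CSU medication "by type of therapy, ATC code, preferred term and symptom treated". Dose is not named.

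**Definition.** SAP 2.4.2 states: "Concomitant medications are defined as any medication given at least once after the first day of first extension study drug dose". A separate listing covers medications that were ongoing at, or started after, the end of the core study and ended before the first extension dose.

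**Stability of background therapy.** Protocol 5.1.2 has patients continue background medication "with a stable regimen during the study". Protocol 5.5.7 words it differently: "It is recommended that patients should remain on a stable treatment regimen".

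**The concern.** QGE031 is given on top of H1-antihistamines, and background and rescue medication both remain allowed after treatment stops. Readers will therefore look to the medication tables to see what else patients were taking in each epoch. Three rules in one section, followed as written, could leave those tables short of what Protocol 9.3 planned:

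- A patient whose only rescue record began earlier would not appear as a rescue user in the eCRF table for the later epoch.
- Background H1-antihistamine may run from the approved dose to four times that dose (Protocol 5.5.7). If the categories used do not carry dose, a change of dose within one drug leaves its ATC code and preferred term as they were.
- A drug given only in the hours after the first injection could fall outside both the concomitant summary and the pre-dose listing. Patients are observed on site for 2 hours after that injection (Protocol 5.5.4), and epinephrine use is recorded on the concomitant medication page (Protocol 5.5.6).

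**Working it through.** The documents give no figure on this point, so there is none to reproduce. The check is a comparison of rules, plus one illustration for the eDiary.

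**1. Rescue rule against its neighbours (SAP 2.4.2)**

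| Item | Counted in an epoch if | Output |
|---|---|---|
| CSU medication | starts or continues | summary per epoch |
| Non-urticaria medication | starts or continues | summary per epoch |
| Surgeries and procedures | starts or continues | summary per epoch |
| Rescue (eCRF) | starts | summary per epoch |
| Omalizumab | starts | listing only |

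Rescue is the only per-epoch summary without the continuing limb. Omalizumab shares the narrower wording, but in a listing a record need appear only once.

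Applied literally to a single open record:

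- Begun in the core study and still open: counted in neither extension epoch.
- Begun in the treatment epoch and still open: counted in treatment, absent from follow-up.
- Carried over, with a further record begun in the epoch: the patient is still counted.

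The undercount is thus confined to patients whose only relevant records began before the epoch. Carry-over is possible: the drug may not be switched between core and extension, and both studies share one database (Protocol 5.5.1 and 8.2). SAP 5.1.3 also does not impute dates from the rescue page, and the documents do not say how a record with an incomplete start date would be placed in an epoch.

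**2. The eDiary tablet count as a backstop**

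SAP 2.4.2 summarizes weekly rescue tablets by study week, whatever the start date. One missing day makes the week missing (SAP 2.4.2 and 2.6.10). Weekly symptom scores are prorated from as few as 4 of 7 days.

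Let p be the chance that a diary day is missing. Assume independent days and the same p for both measures; neither assumption comes from the documents.

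- P(rescue week missing) = 1 − (1 − p)^7
- P(symptom week missing) = P(at least 4 of 7 days missing), binomial

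| Assumed p | Rescue weeks missing | Symptom weeks missing |
|---|---|---|
| 1% | 6.8% | under 0.01% |
| 5% | 30.2% | 0.02% |
| 10% | 52.2% | 0.27% |

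The backstop is real, but far less tolerant of missed entries than the scores it would be read beside. It covers rescue tablets and gives no background dose.

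**3. Background dose**

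Protocol 9.3 names pre-specified categories that include dose, and preferred term. SAP 2.4.2 names type of therapy, ATC code, preferred term and symptom treated. Preferred term is common to both; dose is named only in the protocol. The readable bullets of SAP Section 4 do not mention it. Two bullets there are redacted.

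**4. Day 1**

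Day 1 is the day of the first extension dose (SAP 2.1.2). Take a drug given once on Day 1, after the injection:

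- Concomitant? It was not given after the first day, so no.
- Pre-dose listing? It did not end before the first dose, so no.

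It meets neither definition. The per-epoch tables do not rescue it, because they are tables of concomitant medication as defined.

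**The case against.** The case on the other side is substantial, and most of it stands.

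**Rescue is measured twice.** The eDiary count shows the amount taken in both epochs, which the eCRF table would not. This stands, subject to its missing-day rule.

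**Carry-over may be rare.** Rescue is taken as needed. Protocol Table 6-1 records rescue usage at every visit from 301 and not at Visit 206, and rescue has its own CRF page. That fits visit-level records at least as well as one long open record. The documents do not settle it, so no size can be put on the undercount.

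**Dose may not have been dropped.** SAP 2 and 2.1 refer to Protocol Section 9 as the planned analysis, *type of therapy* is undefined and could carry the protocol's categories, and a redacted bullet in Section 4 could declare the change. What can be said is that the readable SAP does not restate dose.

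**The Day 1 gap has backstops.** Emergency epinephrine for an anaphylactic or anaphylactoid reaction requires stopping study treatment (Protocol 5.6.2), and possible anaphylaxis is adjudicated and listed (SAP 2.5.1.2). The literal gap remains for other drugs given that day, and for epinephrine in the medication table itself.

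**A stronger reading to avoid.** A reader might infer that these tables hide antihistamine use that accounts for the reported response, or that sustained remission is being presented as drug-free. The documents do not support this. Remission is defined by UAS7 of 6 or less, background and rescue are expressly allowed in follow-up (Protocol 3.1), continuing background medication is counted in the CSU table, and no text ties the medication tables to the response analysis.

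**Conclusion.** The point holds as a defect of three reporting rules in SAP 2.4.2. By its wording, the eCRF rescue table omits records carried into an epoch. The readable SAP does not restate the protocol's dose categories for background urticaria medication. A drug given only on Day 1 after the injection meets neither medication definition.

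The size is not known. It depends on how sites enter rescue records, on what *type of therapy* contains, and on the redacted bullets of Section 4. The percentages for missing diary weeks rest on assumed rates and describe the fragility of the backstop, not the undercount.

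No endpoint is shown to be affected. The SAP says of the whole analysis: "No hypotheses will be tested as per the protocol. All the analysis will have a descriptive purpose". In a study of that kind the tables are the result, so a rule that leaves out users or dose information the protocol planned to report is worth correcting. The difference between Protocol 5.1.2 and 5.5.7 is a separate matter of protocol wording.

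**What to change.** In SAP 2.4.2:

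- **(a)** Summarize eCRF rescue medication *starting or continuing during* each epoch, as for the other per-epoch summaries.
- **(b)** Summarize background urticaria medication for each epoch by the Protocol 9.3 categories, including dose; or declare the change in SAP Section 4 and give the reason.
- **(c)** Define concomitant medication as given on or after the first extension dose.

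Separately, Protocol 5.1.2 and 5.5.7 must be reconciled on whether a stable background regimen is required or recommended.

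The cost is SAP wording and, for (b), dose categories in a table that Protocol 9.3 already plans. No visits or assessments are added; this assumes that dose is on the medication CRF, as Protocol 9.3 implies. Reported rescue use in the eCRF table may come out higher.

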2.5 Analysis of the primary objective

The primary objective of this study is to obtain data on the long-term safety and tolerability of QGE031 for 12 months of treatment in CSU patients.

The primary variables which will be analyzed are: for AEs/ Serious Adverse Events (SAEs), ECGs, laboratory assessments, vital signs data and events of special interest such as hypersensitivity reactions, anaphylaxis, cardio-cerebrovascular events, and pre-malignancies and malignancies.

2.5.1 Adverse events

All adverse events which start after the first dose of study medication in the extension study and within 16 weeks of last dose, or events present prior to the first dose of extension study treatment

and increased in severity (within 16 weeks of last dose), will be considered as a treatment emergent adverse events. Treatment emergent adverse events (TEAEs) will be presented overall (including those that started during treatment and follow-up epoch) and those which started during the treatment epoch. Non-TEAEs will be presented for those which started during the follow-up epoch.

Adverse events that started during the core study were reported and analyzed in the core study and will not be included in tables of the extension study unless they become more severe. They will, however, be included in listings with additional collected information (e.g., outcome) as applicable.

Adverse events that started in the core study but became more severe in the extension study will be reported and analyzed as new events.

Treatment emergent adverse events with the number and percentage of patients having any adverse event by system organ class (SOC) and preferred term (PT) will be provided for:

- All adverse events
- Adverse events by maximum severity
- Adverse events suspected by the investigator as study drug-related
- Serious adverse events
- Adverse events leading to permanent discontinuation of study drug (only for treatment epoch)

Also, a separate summary table for most frequently reported TEAEs during the study, by SOC and PT, will be produced. Most frequent TEAEs will be those with their PT representing at least 5% of subjects.

Clinicaltrials.gov and EudraCT

For the legal requirements of ClinicalTrials.gov and EudraCT, two required tables on <on-treatment/treatment emergent> adverse events which are not serious adverse events with an incidence greater than 5% and on <on-treatment/treatment emergent> serious adverse events and SAE suspected to be related to study treatment, will be provided by system organ class and preferred term on the safety set population.

If for a same patient, several consecutive AEs (irrespective of study treatment causality, seriousness and severity) occurred with the same SOC and PT:

- a single occurrence will be counted if there is ≤ 1 day gap between the end date of the preceding AE and the start date of the consecutive AE
- more than one occurrence will be counted if there is > 1 day gap between the end date of the preceding AE and the start date of the consecutive AE

For occurrence, the presence of at least one SAE / SAE suspected to be related to study treatment / non-SAE has to be checked in a block e.g., among AE's in a ≤ 1 day gap block. If at least one SAE is occurring, then one occurrence is calculated for that SAE.

The number of deaths resulting from SAEs suspected to be related to study treatment and SAEs irrespective of study treatment relationship will be provided by SOC and PT.

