11. Onset of clinically significant cardiovascular (such as but not limited to myocardial infarction, unstable ischemic heart disease, NYHA Class III/IV left ventricular failure arrhythmia, uncontrolled hypertension within 12 months prior to visit 206), neurological, psychiatric, metabolic, or other pathological conditions such as but not limited to cerebrovascular disease, neurodegenerative diseases, or other neurological disease, uncontrolled hypo- and hyperthyroidism and other autoimmune diseases, hypokalemia, hyperadrenergic state, or ophthalmologic disorder that could interfere with the compromise the safety of the patients, interfere with evaluation or interpretation of the study results, or preclude completion of the study
12. Medical examination or laboratory findings that suggest the possibility of decompensation of co-existing conditions for the duration of this study. Any items that are cause for uncertainty will be reviewed with the investigator
13. History or current treatment for hepatic disease including but not limited to acute or chronic hepatitis, cirrhosis or hepatic failure or AST/ALT levels or INR of more than 1.5x upper limit of normal (ULN)
14. History of renal disease or creatinine level above 1.5x ULN at visit 206
15. Platelets < 100,000/ μ L at visit 206
16. Long QT syndrome or whose QTcF (Fridericia) measured at end of core study visit (Visit 206) is prolonged (> 450 ms for males or > 460 ms for females) and confirmed by a central assessor (ECG measurement should not be repeated in these patients to confirm eligibility)
17. Pregnant or nursing (lactating) women, where pregnancy is defined as the state of a female after conception and until the termination of gestation, confirmed by a positive hCG laboratory test
18. Women of child-bearing potential, defined as all women physiologically capable of becoming pregnant, unless they are using effective methods of contraception during dosing of study treatment. Effective contraception methods include:
 - Total abstinence (when this is in line with the preferred and usual lifestyle of the subject. Periodic abstinence (e.g., calendar, ovulation, symptothermal, post-ovulation methods) and withdrawal are not acceptable methods of contraception

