7.1 Adverse Events

An adverse event (AE) is any untoward medical occurrence (i.e., any unfavorable and unintended sign [including abnormal laboratory findings], symptom or disease) in a patient or clinical investigation patient after providing written informed consent for participation in the study. Therefore, an AE may or may not be temporally or causally associated with the use of an investigational product.

For all patients who have signed informed consent and are entered into the next epoch (Extension 1 Treatment epoch) of the study, all adverse events occurring after informed consent is signed will be recorded on the Adverse Event CRF.

The occurrence of adverse events should be sought by non-directive questioning of the patient at each visit during the study. Adverse events also may be detected when they are volunteered by the patient during or between visits or through physical examination, laboratory test, or other assessments.

Abnormal laboratory values or test results constitute adverse events only if they fulfill at least one of the following criteria:

- they induce clinical signs or symptoms,
- they are considered clinically significant,
- they require therapy.

Clinically significant abnormal laboratory values or test results should be identified through a review of values outside of normal ranges/clinically notable ranges, significant changes from baseline or the previous visit, or values which are considered to be non-typical in patient with underlying disease. Investigators have the responsibility for managing the safety of individual patient and identifying adverse events. Alert ranges for labs and other test abnormalities are included in [Appendix 1](#) and will be described in the laboratory manual.

Adverse events should be recorded in the Adverse Events CRF under the signs, symptoms or diagnosis associated with them, accompanied by the following information:

- the severity grade
 - mild: usually transient in nature and generally not interfering with normal activities
 - moderate: sufficiently discomforting to interfere with normal activities
 - severe: prevents normal activities
- its relationship to the investigational treatment (no/yes), or
- its duration (start and end dates) or if the event is ongoing an outcome of not recovered/not resolved should be reported.
- whether it constitutes a SAE (see [Section 7.2.1](#) for definition of SAE)
- action taken regarding investigational treatment.

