All adverse events should be treated appropriately. Treatment may include one or more of the following:

- no action taken (i.e. further observation only)
- investigational treatment dosage adjusted/temporarily interrupted
- investigational treatment permanently discontinued due to this adverse event
- concomitant medication given
- non-drug therapy given
- patient hospitalized/patient's hospitalization prolonged
- its outcome (not recovered/not resolved; recovered/resolved; recovering/resolving, recovered/resolved with sequelae; fatal; or unknown)

Once an adverse event is detected, it should be followed until its resolution or until it is judged to be permanent, and assessment should be made at each visit (or more frequently, if necessary) of any changes in severity, the suspected relationship to the study drug, the interventions required to treat it, and the outcome.

Information about common side effects already known about the investigational drug can be found in the Investigator Brochure (IB) or will be communicated between IB updates in the form of Investigator Notifications. This information will be included in the patient informed consent and should be discussed with the patient during the study as needed.

The investigator should also instruct each patient to report any new adverse event (beyond the protocol observation period) that the patient, or the patient's personal physician, believes might reasonably be related to study treatment. This information should be recorded in the

investigator's source documents; however, if the AE meets the criteria of an SAE, it must be reported to Novartis.

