13.1 Appendix 1: Clinically notable laboratory values and vital signs

Refer to [Appendix 2](#) for clinically notable serum blood chemistry tests for hepatotoxicity.

The following specific criteria have been identified for this study:

- AST, ALT or INR above 1.5x ULN
- Creatinine above ULN
- Platelets <75,000 μ L.
- Stool test result positive for ova or parasites

Any patient that has AST, ALT, INR or creatinine levels above the limits specified above or a stool test result positive for ova or parasites at Visit 206, should be excluded from the study.

[figure not shown]
Any patients that have AST, ALT, INR or creatinine levels above the limits specified above, after the patient has started treatment in the extension study, should have regular laboratory assessments to monitor those laboratory parameters, until they return to baseline values (or within normal range), or the investigator indicates that post baseline values are sufficiently close to baseline that no further follow-up is warranted for patient safety.

Any patients that have platelets <75,000 μ L after the patient has started treatment should be discontinued from study drug.

For all other laboratory assessments, the Central Laboratory will flag laboratory values falling outside of the normal ranges on the Central Laboratory Report (which the investigator should review and sign-off) and the investigator will report any values considered clinically significant in the eCRF.

Notable values for vital signs and change from baseline will be summarized. A notable value is defined as follows: heart rate of <40 and >90 bpm; systolic blood pressure of <90 and >140 mmHg; diastolic blood pressure of <65 and >90 mmHg.

For ECGs a notable QTc value is defined as a QTc (Fridericia's) interval of greater than 450 ms for males and > 460 for females – all such ECGs require assessment for clinical relevance by the Investigator. Patients with a heart rate of >100 bpm measured on 2 occasions, approximately 10 minutes apart, while resting, should be discontinued from study treatment.

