> 3 to ≤ 5 x ULN (patient is asymptomatic)	
 Repeat LFT within the next week If elevation is confirmed, initiate close observation of the patient 	Investigator discretion Monitor LFT within 1 to 4 weeks
ALP (isolated)		
> 2 x ULN (in the absence of known bone pathology)	
 Repeat LFT within 48 hours If elevation persists, establish causality Complete liver CRF 	Investigator discretion Monitor LFT within 1 to 4 weeks or at next visit
TBL (isolated)		
> 2 x ULN (in the absence of known Gilbert syndrome)	
 Repeat LFT within 48 hours If elevation persists, discontinue the study drug immediately Hospitalize if clinically appropriate Establish causality Complete liver CRF 	ALT, AST, TBL, Alb, PT/INR, ALP and γGT until resolution ^c (frequency at investigator discretion) Test for hemolysis (e.g., reticulocytes, haptoglobin, unconjugated [indirect] bilirubin)
> 1.5 to ≤ 2 x ULN (patient is asymptomatic)	
 Repeat LFT within the next week If elevation is confirmed, initiate close observation of the patient 	Investigator discretion Monitor LFT within 1 to 4 weeks or at next visit
Jaundice	
 Discontinue the study drug immediately Hospitalize the patient Establish causality Complete liver CRF 	ALT, AST, TBL, Alb, PT/INR, ALP and γGT until resolution ^c (frequency at investigator discretion)
Any AE potentially indicative of	
 Consider study drug 	Investigator discretion

Criteria	Actions required	Follow-up monitoring
a liver toxicity*	interruption or discontinuation 
• Hospitalization if clinically appropriate• Establish causality• Complete liver CRF	

*These events cover the following: hepatic failure, fibrosis and cirrhosis, and other liver damage-related conditions; the non-infectious hepatitis; the benign, malignant and unspecified liver neoplasms

^aElevated ALT/AST > 3 x ULN and TBL > 2 x ULN but without notable increase in ALP to > 2 x ULN

^b(General) malaise, fatigue, abdominal pain, nausea, or vomiting, or rash with eosinophilia

^cResolution is defined as an outcome of one of the following: (1) return to baseline values, (2) stable values at three subsequent monitoring visits at least 2 weeks apart, (3) remain at elevated level after a maximum of 6 months, (4) liver transplantation, and (5) death.

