2.8 Interim analysis

The study is planned with one interim analysis occurring when all patients have completed the treatment epoch. In particular, the summary will include baseline characteristics, adverse events, exposure, concomitant medication, ECG, vital signs, safety laboratory data and the weekly symptom scores, derived responder status, [REDACTED].

Study procedures will not be modified as a result of this interim analysis.

3 Sample size calculation

The sample size calculation is defined in the protocol [\[section 9.7\]](#).

4 Change to protocol specified analyses

- The definition of the safety set (SS) was updated - no additional check needed for subjects “who had at least one post-baseline (Visit 301) safety assessment”.
- Medical history will consist of medical conditions which started before the start of the core study, instead of before the start of the open-label extension study and will therefore only be listed and not tabulated.
- Adjudicated AEs will only be listed and not summarized, since few adjudicated AEs are expected.

[REDACTED]

- [REDACTED]
- [REDACTED]
- The definition of TEAE is updated as: all adverse events which start after the first dose of study medication in the extension study and within 16 weeks of last dose, or events present prior to the first dose of extension study treatment and increased in severity (within 16 weeks of last dose).
- All adverse events which start after the first dose of study medication in the extension study or events present prior to the first dose of extension study treatment and increased in severity, will be considered TEAEs, similar to the core study definition. TEAEs will be summarized by treatment epoch and over all, which will be based on the epoch derivation that depends on the patient's visit dates which might not occur exactly on last dose + 4 weeks.
- For patients with concomitant use of omalizumab, efficacy variables (HSS/ISS/UAS/ [REDACTED]) will be censored at the last visit prior to the date of start of omalizumab and treated as missing onward.
- Only positively adjudicated Cerebrovascular events will be listed.

5 Appendix

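### An AE ongoing at the first extension dose that permanently stops QGE031 at unchanged severity is missing from the AE-discontinuation table

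*SAP*

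**What the plan says.** SAP 2.5.1 lists five TEAE tables by system organ class (SOC) and preferred term (PT). One covers AEs leading to permanent discontinuation of study drug and is restricted to the treatment epoch. An AE counts as treatment-emergent if it starts after the first extension dose and within 16 weeks of the last dose, or if it was already present and its severity rose in that time. AEs that began in the core study "will not be included in tables of the extension study unless they become more severe"; they remain in listings.

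Protocol 9.4.1 has the same exclusion for AEs that began in the core follow-up epoch. SAP Section 4 gives two wordings of the TEAE definition, one with the 16-week limit and one without, and both keep the severity condition.

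Protocol 7.1 grades severity as mild, moderate or severe by interference with normal activities. It records separately "whether it constitutes a SAE" and the action taken, for which one option is "investigational treatment permanently discontinued due to this adverse event". Protocol 5.6.2 requires treatment to stop for an AE when continued exposure would be detrimental. SAP 2.3.1 reports the number who discontinued the treatment epoch, with the reason.

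**The concern.** A severity increase is a sensible test of whether an old AE has become a new one. It is not a test of whether an AE ended treatment. An investigator may dose a patient with an ongoing AE, watch it fail to settle, and then stop QGE031 although the grade has not moved. That stop first happens in the extension. The core study cannot have reported it, and the patient may have received placebo or omalizumab there.

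The primary objective is long-term safety in a single-arm study, so descriptive tables of this kind are the result. The AE-discontinuation table could show fewer patients than disposition counts as stopping for an AE, with nothing to explain the difference.

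**Working it through.** The plan gives no figure for this point, so there is none to reproduce. The check applies the rule to cases and then works out the effect of one patient.

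**Rule applied to an AE ongoing at the first extension dose**

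| Case | Grade rises? | TEAE under SAP 2.5.1? | In AE-discontinuation table? |
|---|---|---|---|
| Moderate, becomes severe, QGE031 stopped | Yes | Yes | Yes |
| Moderate throughout, QGE031 stopped | No | No | No |
| Severe at first dose, QGE031 stopped | Cannot rise on a three-grade scale | No | No |

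**Does another provision bring rows 2 and 3 back?**

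- The non-TEAE tables in SAP 2.5.1 cover only AEs that started in the follow-up epoch, so they do not.
- Listings include the event but give no incidence.
- Disposition (SAP 2.3.1) counts the stop under its reason, without SOC or PT.
- Protocol 7.1 has an AE followed to resolution and reassessed at each visit. It does not tell sites to open a new record when only the action taken changes. A recurrence entered as a new AE would count.
- AEs starting between consent at Visit 206 and dosing at Visit 301 meet the same outcome, through the TEAE definition itself.

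**Effect per patient**

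Inputs: expected enrolment of about 240 (protocol 3.1 and 9.7), and the sample sizes 200, 250 and 300 that protocol 9.7 uses for its graph. Formula: fall in incidence = k/N, where k is the number of patients missed.

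- N = 240, k = 1: 1/240 = 0.42 percentage points
- N = 200: 1/200 = 0.50
- N = 250: 1/250 = 0.40
- N = 300: 1/300 = 0.33

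The documents give no value for k. As an assumed range at N = 240: k = 0 gives 0; k = 1 gives 0.42; k = 2 gives 0.83; k = 3 gives 1.25 percentage points. Because k cannot be negative, the table can only be too low.

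**The case against.** The rule is deliberate. It stands in the protocol, is repeated in the SAP, and SAP Section 4 ties the TEAE approach to the core study. No hypothesis is tested and nothing disappears from the report. Entry criteria also thin out the candidates; protocol 4.2, for example, excludes "Medical examination or laboratory findings that suggest the possibility of decompensation of co-existing conditions for the duration of this study". All of this stands. It bears on the weight of the point, but it does not put the missing row into the table.

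A reader might infer more, in four ways that the documents do not support.

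- **That the liver rules routinely produce such cases.** For isolated bilirubin above 2 x ULN, Table 13-2 says "If elevation persists, discontinue the study drug immediately". That line follows a repeat test within 48 hours, so it confirms an on-study value; it does not describe an elevation carried over from before dosing. The row does not apply to known Gilbert syndrome, and exclusion criterion 13 bars a history of hepatic disease.
- **That persistent tachycardia goes unreported.** Appendix 1 stops treatment for a resting heart rate above 100 bpm on two occasions. However, SAP 2.5.3 already tabulates and lists pulse above 100 bpm in both epochs. What that output lacks is the link to the drug stop.
- **That the SAE table has an equal gap.** The same logic would omit an ongoing AE that first turns serious at an unchanged grade. But protocol 7.2.1 defines an SAE through appearance or worsening, and worsening will normally raise the grade. Deaths are reported by SOC and PT in any case (SAP 2.5.1.3). This deserves a remark only.
- **That a sizeable share of the table is lost.** Any such share needs both an assumed number missed and an assumed number shown. The documents give neither.

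**Conclusion.** The point holds for the AE-discontinuation table, at minor weight. Under SAP 2.5.1 as written, an AE ongoing at the first extension dose that leads to a permanent QGE031 stop without a grade increase is left out, and no other provision supplies its SOC and PT incidence. The clearest route is the general rule in protocol 5.6.2 on detrimental exposure.

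The size is 0.42 percentage points per affected patient at N = 240. The number affected is unknown, probably small and possibly zero. The conclusion assumes that sites update the existing AE record when only the action taken changes, and that increased severity means a higher grade on the protocol 7.1 scale. If sites opened a new record with a new start date, the event would be counted.

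**What to change.** Leave the TEAE definition as it is, so that the other tables stay comparable with the core study. In SAP 2.5.1, define the AE-discontinuation table as all AEs whose recorded action is permanent discontinuation of QGE031 during the extension treatment epoch, regardless of AE onset. Footnote those that began before the first extension dose. Because core and extension records share one database (protocol 8.2), the selection should be tied explicitly to extension dosing.

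For the SAE table, a footnote is enough: name any pre-existing AE that first becomes serious in the extension without a grade increase. This leaves the SAE counts unchanged.

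The cost is a few lines of SAP text and a changed selection rule for one table; action taken is already collected. The SAE footnote may need the date of seriousness from the SAE report. The downside is that the discontinuation percentage may come out slightly higher and the table is no longer strictly TEAE-only, which the footnote makes plain.
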